4.4.1 Time Commitment for Provider Participants by Study Phase

The study duration and number of study visits required of provider participants are shown in the table below for each study activity. Note that for Phase I for both providers and patients, the socio-demographic survey will be completed at the same visit as the qualitative interview or mock training. Providers' interview or mock training sessions will occur at a time when providers are routinely in the clinic or in their offices and do not therefore require a special visit. However, as mentioned previously, 8-16 visits will be recorded with each provider at both baseline (pre-training) and during the patient training visits, totaling 16-32 audio recorded visits for each provider (these numbers are approximate because they depend on individual clinicians' clinic schedules and availability of eligible patients). There is no follow-up in Phase I. The only additional visits necessary for providers to make outside of their regularly occurring schedule are for the in-person component of the training; the educational component can be completed individually at the provider's convenience. In Phase III, providers who did not previously participate in Phase II (and thus have no prior survey data) will be asked to complete a brief socio-demographic survey before recording their first clinic visit.

Time Commitment for Provider Participants by Study Phase				
Study Phase	Activity	# Study Visits	Duration of Activity	Total Duration for Participants
Phase I (Qualitative Study)	
 - Socio-demographic Survey - Qualitative Interview OR Mock Training 	
 1 - - 	
 5 minutes 45 minutes 60-90 minutes 	60-90 minutes
Phase II (Provider Training Study)	
 - Pre-Training Survey - Training: Educational Component - Training: In-person Component - Post-Training Survey - Clinic encounter communication assessment/audio recording (8-16 per provider at baseline; post-training) - 1-Month Follow-up Survey - 6-Month Follow-up Survey 	
 1 - - - 0 	
 15 minutes 60 minutes 60 minutes 20 minutes Minimal additional time 20 minutes 20 minutes 	≤ 18 months
Phase III	- Audio recordings of clinic visits	0	Minimal	

(Patient Training Study)	(16 patients) 
 - Socio-demographic Survey (if provider has not previously completed as part of Phase II baseline) 		additional time 5 minutes	12-18 months
--------------------------	---	--	------------------------------	--------------

4.4.2. Time Commitment for Patient Participants by Study Phase

The study duration and number of study visits required of patient participants are shown in the table below for each study activity.

Time Commitment for Patient Participants by Study Phase				
Study Phase	Activity	# Study Visits	Duration	Total Duration for Participants
Phase I (Qualitative Study) or Exploratory Focus Groups	- Socio-demographic survey - Focus Groups or interview OR Mock Training/Cognitive Interview	1 - -	5 minutes 90 minutes/ 45 minutes 60-90 minutes	60-90 minutes
Phase II (Provider Training Study)	- Clinic visit communication assessment - Post-Clinic Visit Survey	1 - -	5 minutes No additional time for study	60 minutes
Phase III (Patient Training Study)	- Pre-Training Survey - Intervention - Clinic visit audio recorded - Post-Training Survey - 2-Month Follow-up Survey	1 - - - -	46 minutes 30 minutes No additional time for study 31 minutes 41 minutes	≤ 3 months

5.0 Risks to Participants

This study involves participation in qualitative focus groups or interviews, or participation in a behavioral intervention study with minimally invasive assessments (e.g., self-report, collection of audio-recorded clinic visits). The major risks for study subjects are (1) discomfort at answering study questions or during discussions with providers, (2) loss of privacy or confidentiality. Due to the protections we will have in place, we believe these risks to be minimal. There are no procedures that will be conducted as part of the study.

Provider participants will be assured that their participation or the content of their audio recorded clinic visits with patients will not affect their employment in any way. Further, all efforts will be made to conduct the audio recording study with minimal interference to providers' clinical care. We are also making it possible that a clinician can participate even if they do not allow audio recording of their patient encounters.

We are concerned with ensuring that study questions pertaining to sexuality are handled in a sensitive manner. We have chosen standardized sexuality assessment tools that have been widely used and validated to every extent possible, and have made every attempt to ensure that the sexuality items used in the current study are minimally intrusive and highly appropriate. If patients do not want to answer the screening question assessing their degree of sexual concerns or discuss this topic further, they may choose not to answer this question and not to participate in the qualitative or patient training studies (Phases I/III). They will also be informed as to the nature of the items in the study that will be asked of them, and will be assured in the consent forms that they do not have to answer any questions that make them

uncomfortable. We will make it clear that whether or not they answer the screening items or agree to participate in the research study will not affect their care.

6.0 Potential Benefits to Participants

It is possible that the provider and patient training programs will improve providers' and patients' communication skills, and therefore have a beneficial effect on patient-provider interactions, relationships and/or patient health, but this cannot be guaranteed and this will not benefit patients whose providers have not yet participated in the provider training program (i.e., during the qualitative study and the provider baseline phase). Patients receiving the Skills-based training program (Phase III) may also experience benefits including in their interactions with providers and in their relationships or health but this will not affect patients who have not participated in this program (i.e., during the provider training study; patients randomized to the control condition). Patients in either condition in Phase III may learn more about the effects of breast cancer on menopausal and sexual health after reading through the resources. Findings from this study may inform future research on patient-provider communication and sexuality in breast cancer as well as interventions to improve the quality of care for patients with breast cancer and other types of cancer or medical conditions. The minimal risks to subjects are reasonable in relation to potential benefit in improving the care of cancer patients.

7.0 Provisions to Maintain the Confidentiality of Data

In order to minimize the risks associated with discomfort in answering questions, participants will be told that they do not have to answer any research questions and that, if they change their mind about participating, they can stop at any time. All participants (patients and providers) will also be assured that they can stop the audio recording of the encounter at any time, if applicable. All information collected for this study will be kept confidential. Subjects will be told that all information will be kept in strict confidence. All data will be stored on computer files or in locked filing cabinets to which only select members of the research staff will have access. All patient discussions about the study and training sessions will occur in private areas or over the telephone. In order to minimize the risks associated with loss of confidentiality, all patient data (including audio recordings and audio transcripts) will be kept confidential and secure, will be de-identified for analytic purposes, and none of the patients' information will be released to their physician, health care organization, or any other third party without the patient's permission, except as required by law. All audio recordings will be destroyed when analyses are complete or later, if necessary to comply with regulatory authorities.

8.0 Costs to Participants

There are no costs to participants for their participation in the study. The cost of parking, if necessary, will be reimbursed.

9.0 Consent Process

9.1. Consent Process for Provider Participants

Consent from provider participants will be obtained at the following time points: For Phase I (Qualitative Study), in-person immediately before the individual qualitative interview, in the location where the qualitative interview/mock training will be held, by the PI or other consent designee; for Phase II (Provider Training Study), at a convenient time for the provider and in all cases prior to completion of the baseline survey and first clinic visit assessment, by the PI or other consent designee. Participation in Phase III (Patient Training Study) will be included in a separate consent form so as not to confuse participants about what is entailed in their participation. Only English speaking providers will be enrolled.

9.2. Consent Process for Patient Participants

Consent from patient participants will be obtained in written form by an IRB-approved consent designee: For Phase I (Qualitative Study) or the exploratory focus groups, in-person immediately before the focus group/interview, or mock training/cognitive interview at the location where the focus group/interview or mock training/cognitive interview will be held (i.e., a private conference room or other private location on site); for Phase II (Provider Training Study) in-person

before the clinic visit in a private location such as a private clinic room or in a quiet space within the waiting area (or in the case of non-audio recorded clinic encounters, potentially following the clinic encounter); for Phase III (Patient Training Study), electronic consent will be obtained through RedCap or, for patients with no computer access, written consent will be obtained in person or through the mail. Only English speaking patients will be enrolled. Participants will be given time to ask questions privately before they sign consent forms.

10.0 Off-Study Criteria

Any participant may leave the study at any time due to distress or other reasons. It is possible, though very unlikely, that a participant in the focus group might become unruly or disruptive, in which case she would be asked to stop participation. For Phase II and III, a clinician participant may change his or her preference for having the clinic encounters audio recorded, and this will not necessitate leaving the study, although we will have the clinician indicate his or her new preferences in the consent form.

11.0 Drugs and Devices

Not applicable.

12.0 Multi-Site Research Study

Not applicable.

13.0 Statistical Analysis

13.1. Statistical Analyses for Qualitative Study (Phase I) and Exploratory Aim

13.1.1. Primary and Secondary Outcome Variables

Our primary analysis for this study is exploratory using qualitative methods and as such, there are no primary or secondary outcome variables.

13.1.2. Analyses

Demographic information from participants will be analyzed using descriptive statistics (e.g., frequencies, means, variances) to ascertain relevant characteristics of the study group. Primary analyses will be qualitative. Qualitative interviews and focus groups will be transcribed to allow for coding of the dialogue. Data from qualitative interviews and focus groups will be analyzed using qualitative software, which allows text to be coded into a hierarchical, branching structure that first identifies broad concepts, followed by themes and variations within those constructs. Data analysis will utilize a grounded theory approach, in which theory is derived from the data, and new theoretical categories are derived until they are “saturated” and further insights do not emerge.⁸⁴ In this theoretical approach, the researcher interprets and labels verbatim quotes pertaining to the subject under inquiry (i.e., “raw data”) and codes concepts that form the basic units of analysis. Concepts that pertain to similar phenomena are then classified into categories which provide the cornerstones of a developing theory. Finally, through constantly comparing concepts and categories, analyzing data for patterns, and testing and revising hypotheses, a theory emerges from the data. Another approach that may also be utilized, depending on the fit with the data, is the framework approach to qualitative analysis,⁸⁵ which is useful for targeted qualitative studies, as the exploratory focus groups are in the current study (e.g., in developing an intervention rather than serving to develop a unified generalizable theory). [name] has familiarity in conducting qualitative analysis and will utilize the expertise of other research team members in coding the data. Two coders will code and/or discuss all data and differences will be resolved through discussion. Regular meetings among the qualitative coding team will be held to ensure a high level of quality for the qualitative analysis. Mock training and cognitive interview notes will be examined descriptively rather than using grounded theory methods. Study team meetings will help translate the findings of the qualitative focus groups and interviews to intervention content drafts; these will be reviewed and finalized through an iterative process utilizing appropriate expertise within the study team.

13.2. Outcomes and Statistical Analyses for Provider Training Study (Phase II)

13.2.1. Primary Outcomes

- (1) providers' **self-efficacy** and **outcome expectancies** for communicating about sexual concerns (physical, motivational/emotional, or either) on a 0-10 point Likert scale where 0=not at all confident or will not improve at all and 10=extremely confident or will improve a lot,
- (2) **frequency of 2 critical provider behaviors**^{86,87} per visit obtained from audio recordings: (a) Asking a question about sexual concerns, and (b) Offering information/counseling pertaining to sexual concerns, and
- (3) 2 aspects of **quality of communication**: (a) Complexity (i.e., number of target behaviors provider engaged in; and (b) Length of discussion about sexual concerns (in seconds), obtained through audio recorded sessions.

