2.3. Research Hypothesis

2.3.1. Hypothesis I.

We expect that the frequency and quality of provider communication about sexuality will increase following provider training.

2.3.2. Hypothesis II.

We expect that the Skills-based patient training program will be feasible and acceptable and that patients will report increased pre- to post-training beliefs and improved sexual function and other health outcomes at 2-month follow-up compared to the Control condition.

2.3.3. Hypothesis III.

We expect that patients receiving the Skills-based training will be more likely to ask a question pertaining to sexuality and raise the topic of sexuality than patients in the Control condition.

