
Descriptive analyses (e.g., frequencies, measures of central tendency) will determine the feasibility and acceptability of the training program. Seventy-five percent of participants rating the training program favorably ("Agree"/"Strongly

Agree" or "Satisfied"/"Very Satisfied") on study evaluations will be considered adequate acceptability. Patients at baseline and post-intervention will be compared on socio-demographic and medical variables using Chi-square tests or t-tests. Pilot efficacy analyses will be calculated through the following method. Mean differences will be calculated in self-report outcome measures at baseline and 6-month follow-up as the final endpoint, along with standard deviations and the effect size (mean difference/SD of the differences). Regarding the communication outcomes, if audio recordings are available, those data will be used. If there appear to be significant differences between the audio recorded and the self-report communication data, separate analyses may be conducted for these two types of data. Clinician communication outcomes will be examined descriptively by comparing the proportions of clinic visits in which the target communication behaviors occurred at post-intervention versus baseline. Additionally, we will conduct exploratory analyses on the communication variables where the effect of post-intervention was evaluated using generalized linear models with robust standard errors via Generalized Estimating Equations to account for within-provider correlation. Specifically, logistic regression will be used to examine binary outcomes, Poisson regression will be used to examine length of discussion about sexual health and a risk ratio presented for this variable (no discussion was coded as zero seconds), and ordinal logistic regression will be used to examine intervention effects on complexity of communication (categorized as 0, 1, or 2) and on patient satisfaction. Although the study was not powered for formal comparisons, we will consider presenting the model based estimates of effect sizes and corresponding 95% confidence intervals.

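### Both Phase II quality-of-communication outcomes are analysed over all visits, so they mix quality with how often sexual health is discussed

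*Combined protocol and SAP*

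**What the plan says.** Hypothesis I (section 2.3.1) reads: "We expect that the frequency and quality of provider communication about sexuality will increase following provider training". Section 13.2.1 accordingly lists frequency and quality as separate primary outcomes for the Provider Training Study. Frequency concerns two provider behaviours: "a) Asking a question about sexual concerns, and (b) Offering information/counseling pertaining to sexual concerns". Quality has two parts: "Complexity (i.e., number of target behaviors provider engaged in; and (b) Length of discussion about sexual concerns (in seconds".

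Section 13.2.3 sets out the analyses. Frequency is handled descriptively, by "comparing the proportions of clinic visits in which the target communication behaviors occurred at post-intervention versus baseline". Exploratory models that allow for within-provider correlation follow. For complexity, "ordinal logistic regression will be used to examine intervention effects on complexity of communication (categorized as 0, 1, or 2". For length, "Poisson regression will be used to examine length of discussion about sexual health", reported as a risk ratio, with the note that "no discussion was coded as zero seconds".

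The same section says that coding starts by recording whether sexual health was discussed at all, so the indicator needed to separate visits with and without a discussion will exist. No Phase II analysis of complexity or length restricted to visits with a discussion is planned, and no two-part model. Zero-inflated models are mentioned only for the Phase III question count (section 13.3.3).

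**The concern.** The hypothesis makes two claims, so the quality outcomes should be able to show something that the frequency outcomes do not. As planned, they include every visit, and a visit without a discussion scores zero on both. If training led providers to raise the topic more often, in the same way and for the same time as before, both quality measures would rise.

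At stake is the interpretation of named primary outcomes: a report could describe better discussions when only their number had changed. Section 13.2.4 also says that pre-post effect sizes will inform a larger trial. It does not say which outcomes will be used, so that consequence is possible rather than certain.

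**Working it through.** Phase II states no power, alpha or target effect, so there is no figure of the plan's own to reproduce. The check rests on two identities.

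**1. Complexity.** Inputs: the two behaviours in section 13.2.1 and the 0/1/2 scale in section 13.2.3. If complexity counts those two behaviours, then for each visit complexity = (asked: 0 or 1) + (offered information: 0 or 1), and so

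mean complexity = P(ask) + P(offer).

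The mean adds nothing to the two proportions. The distribution adds co-occurrence. With P(ask) = P(offer) = 0.30, visits could be 70% zero and 30% two, or 40% zero and 60% one. Both have mean 0.6.

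**2. Length.** With zero seconds for visits without a discussion,

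mean length = P(discussion) × mean length given discussion,

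so the length ratio = (ratio of discussion frequencies) × (ratio of durations per discussion).

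**3. Illustration: only frequency changes.** Assumptions not taken from the documents: discussion goes from 30% to 45% of visits; within a discussion P(ask) = 0.5 and P(offer) = 0.7, independent; mean duration 60 seconds throughout.

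- Length: 0.30 × 60 = 18 s to 0.45 × 60 = 27 s; ratio 1.5. The ratio is the same whatever the fixed duration.
- Mean complexity: 0.30 × 1.2 = 0.36 to 0.45 × 1.2 = 0.54.
- At least one behaviour: P given discussion = 1 − 0.5 × 0.3 = 0.85, so 0.255 to 0.3825; odds ratio (0.3825/0.6175)/(0.255/0.745) = 1.81.
- Both behaviours: P given discussion = 0.35, so 0.105 to 0.1575; odds ratio (0.1575/0.8425)/(0.105/0.895) = 1.59.
- Among visits with a discussion, the length ratio and the complexity odds ratios are 1 by construction.

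**4. Range, same within-discussion assumptions.**

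| Discussion, baseline to post | Length ratio | OR, at least one behaviour | OR, both |
|---|---|---|---|
| 10% to 20% | 2.00 | 2.20 | 2.08 |
| 20% to 30% | 1.50 | 1.67 | 1.56 |
| 20% to 40% | 2.00 | 2.52 | 2.16 |
| 30% to 50% | 1.67 | 2.16 | 1.81 |
| 30% to 60% | 2.00 | 3.04 | 2.27 |

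**5. The same ratio from the other cause.** With discussion fixed at 30% and duration doubling from 60 to 120 s, the ratio is (0.30 × 120)/(0.30 × 60) = 2.00, identical to 20% to 40% with no change in duration. The planned model cannot tell these apart.

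**6. Are zeros common enough to matter?** The Phase III planning figures (section 13.3.4) have 30% of visits raised by the provider and, in the control arm, 22% of the other 70% raised by the patient: 0.30 + 0.70 × 0.22 = 0.454. That implies some discussion in about 45% of visits with trained providers and zero seconds in about 55%. It makes the illustrative 45% plausible; the 30% baseline remains an assumption.

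**The case against.** The other side has several good points.

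- **Complexity is not redundant.** A reader might infer that it carries no information beyond the two frequencies. That is true only of its mean. The ordinal model uses the distribution, which also reflects whether a provider both asks and informs in one visit.
- **Length is not frequency under another name.** Seconds are measured separately and a real change in duration moves the ratio. The fault is that the two components are not separated.
- **The frequency change is not concealed.** If discussions became more common but one third shorter, the length ratio would be 1.5 × 2/3 = 1.0, and a reader might infer that both changes vanish. They do not: the planned proportions for each behaviour would still rise, and shorter discussions could be suspected. The suspicion cannot be turned into a figure, because the proportion with either behaviour is not the proportion with any discussion.
- **The identity of the behaviours is inferred.** Section 13.2.1 does not say that complexity counts the two frequency behaviours, and section 13.2.2 lists two further coded ones as secondary. The 0/1/2 scale and the wording "comparing the proportions of clinic visits in which the target communication behaviors occurred at post-intervention versus baseline" make the inference likely, not certain.
- **The models are exploratory.** Section 13.2.3 says so and disclaims power for formal comparisons. No rule exists by which the quality half of Hypothesis I would be declared confirmed.
- **Restricting to visits with a discussion has its own weakness.** Training may add brief discussions where there were none, lowering the median length although no patient received less. Numbers are also small: of the minimum 48 baseline visits (section 4.3.2), 30% is about 14. Coding zero for all visits is a defensible way to measure total communication.

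All of these stand as limits. None supplies an analysis that separates quality from frequency.

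**Conclusion.** The point holds in a limited form. Both quality outcomes are analysed over all visits in a way that mixes in frequency, and nothing planned for Phase II separates them. The size depends on how far discussion frequency moves: for length, a frequency-only change passes straight into the ratio (1.5 for 30% to 45%); for complexity, the odds ratios in that example are 1.81 and 1.59. These rest on illustrative frequencies and within-discussion probabilities. The complexity part also rests on the inferred identity of the two behaviours; the length identity does not.

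The documents do not support the stronger conclusions that the quality outcomes are worthless or that the plan would formally confirm a false quality claim. This is a matter of labelling and of one missing descriptive analysis in an unpowered pilot. It is worth correcting because the outcomes are primary, quality is a distinct hypothesis, and a larger sample would not cure the mixing.

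**What to change.** In section 13.2.3:

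1. State which behaviours complexity counts.
2. Describe the all-visit complexity and length results as total amount of communication, and keep them.
3. Beside them, report for baseline and post-training the proportion of visits with any sexual-health discussion and, among those visits, the length and the complexity distribution (0, 1, 2).
4. State that a gain in quality separate from frequency will not be claimed on the all-visit results alone.
5. Call the figures among visits with a discussion supplementary and descriptive, because they rest on few visits and the patients with discussions may differ before and after training.
6. Label them as added after data collection if Phase II data have already been seen. Sections 4.3.3 and 13.3.3 refer to Phase II results or preliminary data, so this may apply.

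The cost is a few sentences and one table. The discussion indicator, length and behaviours are already to be coded, so no new data are needed.
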